4.4.6 Subgroup Analyses

Subgroup analyses will be performed to assess the impact of select baseline characteristics (see [Table 1](#)) on the change from baseline in percentage of FVC at 52 weeks, by examining the interaction with the study drug with use of the MMRM model. Each baseline factor will be analyzed separately. Some categories may be grouped to allow sufficient sample size for interpretation.

Table 1 Subpopulation Definitions

Baseline Characteristics	Categories
Geographic region	U.S. ROW
Age at randomization	< 65 years ≥ 65 to < 75 years ≥ 75 years
Sex	Female Male
Race/ethnicity	White Nonwhite
Time from IPF diagnosis to randomization	< 1 year ≥ 1 year
Baseline %FVC	< 55% predicted 55% to < 75% predicted ≥ 75% predicted
FEV ₁ /FVC	< 0.80 ≥ 0.80
Hgb-corrected DL _{CO} (% predicted) ^a	< 35% 35% to < 50% ≥ 50%
GAP Index (see Appendix 6)	I/II or III
Extent of fibrosis on HRCT at baseline, expressed as a QLF score	Divided at the median for initial summary score
Periostin	< 50 ng/mL ≥ 50 ng/mL
Duration of prior pirfenidone exposure (for Cohort B only)	0 (started after informed consent) < 1 year ≥ 1 year

FEV₁=forced expiratory volume in 1 second; FVC=forced vital capacity;
HRCT=high-resolution computed tomography; QLF=quantitative lung fibrosis; ROW=rest of world.

Note: Hispanic/Latino ethnicity grouped with nonwhite for subgroup analyses.

4.5 PHARMACOKINETIC ANALYSES

Individual and mean serum lebrikizumab concentration-versus-time data will be reported. During the treatment period, mean concentrations will be reported at Weeks 1, 4, 12, 24, 36, and 52 ($C_{\min,Wk1}$, $C_{\min,Wk4}$, $C_{\min,Wk12}$, $C_{\min,Wk24}$, $C_{\min,Wk36}$, C_{Wk52} , respectively). Estimates for these parameters will be tabulated and summarized (mean, standard deviation, coefficient of variation, median, minimum, and maximum). Additional PK analyses during the treatment period or the 18-week safety follow-up period may be conducted as appropriate. Population PK modeling may be performed to characterize inter-individual variability, which may be reported separately from the CSR.

Pharmacokinetic analysis will use actual times, if available. If actual times are missing, nominal times may be used or data with missing collection times may be excluded.

4.6 BIOMARKER ANALYSES

4.6.1 Pharmacodynamic Biomarker Analyses

The pharmacodynamic (PD) effect of lebrikizumab in IPF will be explored by measuring the levels of biomarkers, focusing on serum levels of chemokines (chemokine ligand [CCL]13, CCL17, and CCL18), and periostin. Other biomarkers of interest may be explored depending on data availability. All PD analyses will be conducted on the ITT population.

Pharmacodynamic marker measurements over time will be summarized graphically and will include median measurements, median absolute changes from baseline, and median percent changes from baseline by treatment group.

4.7 SAFETY ANALYSES

Safety analyses will be based on all patients who received at least one dose of randomized study drug, with patients grouped according to the actual treatment received. Safety summaries will be presented by treatment arm for all treated patients. In addition, safety listings will be provided for any events reported during pirfenidone exposure following informed consent on this study but prior to randomization.

Safety will be assessed through the summary of AEs, laboratory test results (including antibodies to lebrikizumab), ECG, and vital signs. These summaries will be produced separately for each cohort for the treatment period (placebo-controlled study treatment period including safety follow-up period for Cohort B patients or Cohort A patients not entering open label extension period and Cohort A open-label lebrikizumab period including the subsequent safety follow-up period).

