4.3.3 Dosage, Administration, and Compliance

4.3.3.1 Lebrikizumab and Placebo (Cohort A)

Patients in Cohort A and Cohort B who meet all eligibility criteria will be randomly assigned to receive lebrikizumab 250 mg or placebo Q4W for the 52-week placebo controlled period.

Treatment with lebrikizumab or placebo will be by SC injection in the arm, thigh, or abdomen. All patients will receive a total of two injections per dosing visit. Each injection should be administered in a separate location at least 10 cm from the other injection site at each dosing visit. Study sites will be asked to record each injection site. Patients will be monitored for a minimum of 1 hour after dosing for the first three treatment visits and for 30 minutes for all subsequent treatment visits. Each patient will receive a minimum of 13 doses (2 injections per dose) of study treatment during the placebo-controlled, blinded, study treatment period. Patients in Cohort A who enrolled in the study prior to this amendment may receive up to 31 doses of blinded study treatment based upon previous version of this protocol. No dosage modification is permitted during the study.

Patients in **Cohort A** will receive an additional 52 weeks of open-label lebrikizumab (13 doses) in the open-label lebrikizumab treatment period after completion of the placebo controlled period.

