5.1.3 Other Area of Interest: Immunogenicity

As with administration of any exogenous protein, a potential exists for the development of ATAs to lebrikizumab, which could have neutralizing or sensitizing effects resulting in reduced efficacy or safety. Data obtained to date in completed clinical trials do not suggest increased incidence of ATAs with lebrikizumab treatment. In the few patients with positive post-treatment ATA assessments in completed trials, no clinically detectable response as assessed by PK, efficacy, or safety data was seen. A positive antibody response to PLB2 has been observed in asthma patients treated with the previous clinical trial material containing higher levels of PLB2. The clinical significance of the antibody response is not known, and no clinically important safety signals have been identified in completed studies. Refer to the Lebrikizumab IB for more detail.

To assess for the development of immunogenicity, antibody samples will be obtained at baseline, at regular intervals during treatment, and during the safety follow-up period (see [Appendix 1](#), [Appendix 2](#), [Appendix 3](#), and [Appendix 4](#)). Antibody response to lebrikizumab and PLB2 will be assessed.

To ensure that an accurate assessment of immunogenicity is obtained, a final antibody sample will be obtained from all patients at the final visit, whether that occurs at study completion or early discontinuation. With the exception of patients who withdraw from the study early, this sample will typically be obtained following completion of a 14-week follow-up period, which will allow the drug to clear for ≥ 5 half-lives.

Samples will be stored appropriately for further evaluation as needed.

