Appendix 4 Schedule of Assessments: Safety Follow-Up Period (cont)

WEEK post last dose	4 ^a	12	18 (final visit)
Day post last dose (assessment window)	28 (± 3)	84 (± 3)	126 (± 3)
Visit	SFU1	SFU2	SFU3
Optional RNA sample ^m	x		
Concomitant medications	x	x	x
Adverse events ^{a,n}	x	x	x
PFD dispensing (Cohort B only)	x	x	

[figure not shown]
6MWT=6-minute walk test; ATAQ-IPF=A Tool to Assess Quality of Life in IPF; Borg CR10=Borg Category Ratio 10 Scale®; DL_{CO}=diffusion capacity of the lung for carbon monoxide; ECG=electrocardiogram; EOT=end of treatment; EQ-5D=EuroQol 5-Dimension Questionnaire; ET=early termination; HRCT=high-resolution computed tomography; IPF=idiopathic pulmonary fibrosis; SGRQ=St. George's Respiratory Questionnaire; UV=unscheduled visit.

[figure not shown]
- ^a For patients in Cohort A who only complete the placebo controlled study period at Week 52 and choose to discontinue, the Week 52 visit will count as this visit. For patients in Cohort A who complete the open-label lebrizumab study period at week 52OL, the Week 52OL will count as this visit. For patients in Cohort B who complete the placebo controlled study period at Week 52, the Week 52 visit will count as this visit.
- ^b New or worsening abnormalities should be recorded on the Adverse Event eCRF.
- ^c Respiratory rate, pulse rate, systolic and diastolic blood pressure while the patient is in a seated position, and temperature.
- ^d ECGs should be performed prior to any scheduled study procedures (e.g., vital sign measurements, blood draws, and study drug administration, if applicable).
- ^e The Borg CR10 Scale will be performed immediately before and after the 6MWT.
- ^f Complete before all other non-PRO assessments and before the patient receives any disease-status information or study treatment during the study visit.
- ^g Includes RBC count, WBC count, hemoglobin, hematocrit, platelet count, and WBC differential count (neutrophils, bands, lymphocytes, eosinophils, basophils, monocytes, and other cells).

[figure not shown]
Appendix 4

[figure not shown]
Schedule of Assessments: Safety Follow-Up Period (cont)

[figure not shown]

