Patients in Cohort A who had not prematurely discontinued study treatment could continue into the 52-week open-label lebrikizumab treatment period. All patients who continued into the 52-week open-label lebrikizumab treatment period would receive SC lebrikizumab at a dose of 250 mg every 4 weeks. All patients were followed for safety for 18 weeks after the last dose of study treatment.

See the protocol for details in eligibility criteria and study assessments.

Figure 1 Cohort A Study Schematic

d = day; EOT = end of treatment; FVC = forced vital capacity; Lebri = lebrikizumab; n = number of patients; PBO = placebo; SFU = safety follow-up; wk = week.

[figure not shown]
Cohort B (Combination Therapy)

Approximately 330 patients were to be randomized 1:1 to either lebrikizumab 250 mg or placebo every 4 weeks in combination with pirfenidone for a total of 52 weeks. Patients were to be treated daily with the maximum tolerated dose of pirfenidone ≤2403 mg/d.

Patients who provided written informed consent would commence a screening period, which would last approximately 28 days to establish entry criteria. Study treatment would be administered by SC injection every 4 weeks, with the first injection occurring at the randomization visit (Day 1/Visit 2). Patients would continue to receive blinded study treatment every 4 weeks during the placebo-controlled treatment period for a total of 13 doses (26 injections) of blinded treatment. All patients would be followed for safety for 18 weeks after the last dose of study treatment.

See the protocol for details in eligibility criteria and study assessments.

Figure 2 Cohort B Study Schematic

1

d=days; EOT=end of treatment; FVC=forced vital capacity; Lebri=lebrikizumab; n=number of patients; pbo=placebo; PFD=pirfenidone; SFU=safety follow-up; wks=weeks.

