4.7.2 Adverse Events

Verbatim descriptions of treatment-emergent adverse events (TEAEs) will be coded with use of the latest version of Medical Dictionary for Regulatory Activities (MedDRA) dictionary, and their incidence summarized for each treatment arm by system organ class (SOC) and preferred term. A TEAE is defined as any new AE reported, or any worsening of an existing condition reported on or after the first dose of study drug. In addition, separate summaries will be provided for TESAEs, deaths, and AEs leading to discontinuation of study drug.

Analyses will be performed by treatment group for events of special interest that include anaphylactic reactions, local injection-site reactions, infections, and malignancies.

- Anaphylactic reactions will be reviewed and adjudicated by the iACC.
- Local injection-site reactions will be identified with use of the MedDRA high-level term of “injection site reaction”.
- Infections, as identified with use of the MedDRA SOC of “infections and infestations”.
- Malignancies, as identified on the basis of the Standardized MedDRA Queries (SMQ) of “Malignancy”.

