4.7.3 Laboratory Data

Serum chemistry and hematology, evaluations will be summarized by descriptive statistics for each treatment group, together with changes from baseline (Visit 2 value). In addition, all chemistry, hematology, urinalysis, and coagulation data outside the normal reference ranges will be tabulated in terms of the number and proportion of patients with values that are out of range. The toxicity grade at baseline and the highest toxicity grade during the placebo-controlled treatment phase for select labs (eosinophils absolute count, hemoglobin, WBC, platelets, alanine aminotransferase, aspartate aminotransferase, bilirubin, creatine kinase) will be summarized by treatment group.

The number and percentage of patients with positive serum antibodies at baseline and during the study will be tabulated.

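### Cohort A safety tables mix 52-week, 66-week and other observation windows, and event outputs have no time-at-risk denominator

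*Combined protocol and SAP*

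**What the plan says.** SAP 4.7 produces safety summaries separately by cohort and period. The placebo-controlled period is taken as "including safety follow-up period for Cohort B patients or Cohort A patients not entering open label extension period"; the other period is the "Cohort A open-label lebrikizumab period including the subsequent safety follow-up period". SAP 2 states for Cohort A: "All patients were followed for safety for 18 weeks after the last dose of study treatment". Protocol Appendix 4, footnote a, makes Week 52 double as the first follow-up visit for those who finish there ("the Week 52 visit will count as this visit"), which leaves 14 weeks of follow-up after it.

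For adverse events, SAP 4.7.2 has "their incidence summarized for each treatment arm by system organ class (SOC) and preferred term". A treatment-emergent event is anything from the first dose onward, with no end date. For laboratory data, SAP 4.7.3 has values outside the reference range "tabulated in terms of the number and proportion of patients with values that are out of range", and antibody results as the number and percentage of patients positive. SAP 4.7.1 measures exposure from first to last dose and by dose count, which leaves out follow-up time.

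Three other places bear on the window:
- SAP 4 says, in the paragraph on the primary analysis, that analyses take assessments up to Week 52.
- Protocol 6.5 does not mention follow-up in its safety summary periods, but SAP 1 says that the SAP's analysis plan supersedes the protocol's.
- Protocol 4.3.3.1 says that Cohort A patients enrolled before the amendment "may receive up to 31 doses of blinded study treatment based upon previous version of this protocol".

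**The concern.** A crude percentage of patients with an event rises with the time over which they are watched. Here that time depends on a decision made after randomisation. Only Cohort A patients who have not stopped treatment may enter the extension (SAP 2), and entering it removes 14 weeks from the patient's placebo-controlled record. Two patients with the same underlying risk can thus sit in one table with windows that differ by 27%.

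The period tables will also be read side by side. Placebo-controlled and open-label results, or Cohort A and Cohort B results, would differ at the same hazard because their windows differ. In Cohort B follow-up is counted for everyone, so a completer always contributes 66 weeks. Infections are the natural example, because protocol 5.1.1.3 already reports a Cohort A imbalance in them.

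Immunogenicity has a related problem. Protocol 5.1.3 relies on a late sample for an accurate assessment: "this sample will typically be obtained following completion of a 14-week follow-up period, which will allow the drug to clear". In the Cohort A placebo-controlled summary that sample exists only for non-entrants, so one antibody-positive percentage would mix patients with and without it.

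**Working it through.** **1. Reproduce the plan's durations.** Thirteen doses every 4 weeks from Day 1 put the last dose at (13 − 1) × 4 = Week 48. Adding 18 weeks gives 48 + 18 = 66 = 52 + 14. With the open-label year, 52 + 48 + 18 = 118. Protocol 3.2 gives 66 weeks (Cohort B) and 118 weeks (Cohort A), so both agree.

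**2. Windows under SAP 4.7.**
- Cohort A, enters extension: 52 weeks.
- Cohort A, Week 52 non-entrant: 66 weeks; 66/52 = 1.27.
- Cohort A, stops early and goes straight to follow-up: last dose + 18 weeks. For example, a last dose at Week 12 gives 30 weeks.
- Cohort A, 31 blinded doses: last dose (31 − 1) × 4 = Week 120, end-of-treatment visit Week 124, follow-up to Week 138.
- Cohort A open-label period: 52 + 14 = 66 weeks.

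**3. Effect of window length.** Assume a constant hazard and treat a percentage as a 52-week risk p. Then risk over w weeks = 1 − (1 − p)^(w/52).
- Infections, placebo: 41/76 = 53.9% (protocol 5.1.1.3). Over 66 weeks, 1 − 0.461^(66/52) = 62.6%. Over 30 weeks, 36.0%.
- Injection-site reactions, placebo: 6/76 = 7.9% (protocol 5.1.1.1). Over 66 weeks, 9.9%.

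Protocol 5.1.1.3 does not say what window lies behind its infection percentages, so these figures illustrate the mechanism and do not correct the reported results.

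**4. Effect between randomised arms.** Take the same hazard in both arms and let f be the proportion not entering the extension. The crude percentage is (1 − f) × 53.9 + f × 62.58. With f = 10% in one arm and 30% in the other, the spurious difference is 0.20 × 8.68 = 1.7 points. For the 7.9% risk it is 0.4 points. The limit, 0% versus 100%, is 8.7 and 2.0 points. The documents do not give extension uptake by arm.

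**5. Scheduled post-baseline tests per period, before later follow-up visits** (protocol Appendices 1 and 2; ECG also in 4.5.14.1).
- Urinalysis: 4 placebo-controlled (Weeks 12, 24, 36, 52) versus 8 open-label.
- Haematology: 7 versus 8.
- ECG: 2 versus 1.
- Antibodies: 5 versus 4.

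The chance of at least one out-of-range result in k independent tests is 1 − (1 − q)^k. The documents give no q. At an assumed 5% per test (range 2% to 10%), urinalysis gives 18.5% (7.8% to 34.4%) for 4 tests and 33.7% (14.9% to 57.0%) for 8. For ECG and on-treatment antibodies the schedule pushes the other way.

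**The case against.** The strongest reply is that the randomised comparison is largely protected. Both arms follow one rule, the SAP plans no test of placebo-controlled against open-label data, and nothing in the documents shows that entry or stopping differed by arm. That stands, and it limits the point.

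The SAP is also not confined to crude event percentages. SAP 4.7.3 and 4.7.4 give descriptive statistics with changes from baseline, and the worst-toxicity-grade table is already limited to the placebo-controlled treatment phase. If the Week 52 sentence in SAP 4 governed safety, the gap between 52 and 66 weeks would close. It sits with the primary analysis, however, and 4.7 is specific, so the plan has to say which applies.

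Cohort A was unblinded in May 2016 (protocol 1.4), before SAP Version 2 was signed in September 2017, so any new Cohort A table is post hoc. An entrant cannot have a drug-free sample for the placebo-controlled period, and wording cannot create one; it can only stop the two kinds of sample being pooled. Assigning late events to the last treatment period is defensible too, which is a reason to keep the existing table.

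A reader might infer that unequal windows explain the reported infection imbalance (65.4% versus 53.9%), or that open-label percentages must come out higher. The documents support neither. The infection window and uptake by arm are not given, entrants are selected for having stayed on treatment, and test counts differ in both directions. An out-of-range urinalysis is also not the same thing as a urinary tract infection adverse event.

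**Conclusion.** The point holds as a low-cost improvement and does not invalidate the Cohort A safety comparison. Cohort A windows are unequal by construction, the event outputs have no time-at-risk denominator, and SAP 4 and 4.7 disagree on the cut-off. The likely effect between arms is a point or two for a common event, and less for a rare one, unless extension entry differs sharply. Comparisons across periods or cohorts are more exposed: up to 8.7 points for a 53.9% risk at an unchanged hazard. These sizes rest on a constant hazard and on reading the reported percentages as 52-week risks, neither of which the documents confirm. In Cohort B there is no entrant/non-entrant gap, but early stoppers still have shorter windows, so patient-time is useful there as well.

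**What to change.** 1. Reconcile SAP 4 with SAP 4.7. For Cohort A, keep the existing table and add one with a common cut-off: from first dose to the earliest of the Week 52 visit (Day 368, the limit already used in SAP 4.4.3, if there is no such visit), the first open-label dose, or the last study contact. Put later follow-up events in a separate table.
2. In SAP 4.7.2, add patient-years at risk and exposure-adjusted rates per 100 patient-years beside the percentages for treatment-emergent events, serious treatment-emergent events and events of special interest, by period and arm, in both cohorts. This is needed as well as the cut-off, because early stoppers who leave still have less time in the table.
3. In SAP 4.7.3, show out-of-range laboratory values by scheduled visit or per test performed wherever periods are compared.
4. Report antibody positivity separately for on-treatment samples and for post-clearance follow-up samples, with patients sampled as the denominator.

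Label the Cohort A re-tabulation as specified after that cohort's unblinding; it can go into the complete-data analysis described in protocol section 6. The cost is SAP wording and a few extra tables, with no new data collection.

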4.7.1 Exposure of Study Drug

Exposure of study drug (lebrikizumab or placebo) will be summarized descriptively (mean, standard deviation, median, and range) for the following measures:

- Treatment duration [days]=(date of last administration – date of first administration + 1), where the date of first administration is the Visit 2 date
- Number of doses=total number of non-zero doses

4.7.2 Adverse Events

Verbatim descriptions of treatment-emergent adverse events (TEAEs) will be coded with use of the latest version of Medical Dictionary for Regulatory Activities (MedDRA) dictionary, and their incidence summarized for each treatment arm by system organ class (SOC) and preferred term. A TEAE is defined as any new AE reported, or any worsening of an existing condition reported on or after the first dose of study drug. In addition, separate summaries will be provided for TESAEs, deaths, and AEs leading to discontinuation of study drug.

Analyses will be performed by treatment group for events of special interest that include anaphylactic reactions, local injection-site reactions, infections, and malignancies.

- Anaphylactic reactions will be reviewed and adjudicated by the iACC.
- Local injection-site reactions will be identified with use of the MedDRA high-level term of “injection site reaction”.
- Infections, as identified with use of the MedDRA SOC of “infections and infestations”.
- Malignancies, as identified on the basis of the Standardized MedDRA Queries (SMQ) of “Malignancy”.

